2.1.5 Immunogenicity endpoints

2.1.5.1 Anti-drug (efpeglenatide) antibody

Blood samples are taken to assess the Anti-drug antibody (ADA) status (positive/negative) and level (titer) at Visit 2/Week 0, Visit 4/Week 4, Visit 6/Week 12, Visit 9/Week 30, at the end of treatment visit, and 6 weeks post-treatment follow up visit.

2.1.6 Pharmacokinetic endpoints

Pharmacokinetic variables include the concentration of efpeglenatide in the efpeglenatide groups:

- Serum C_{trough} of efpeglenatide at pre-dose (Weeks 4, 12, 24, 30);
- Serum concentration of efpeglenatide at post-dose (either 4 days [± 1 day] after first IMP dose, 4 days [± 1 day] after 4th dose, or 4 days [± 1 day] after 12th dose in a subset of

participants). All valid samples collected will be sent to the laboratory to be analyzed, even if out of the specified window.

2.1.7 Pharmacodynamic/genomics endpoints

Pharmacodynamic parameters are not evaluated in this study.

2.2 DISPOSITION OF PARTICIPANTS

This section describes participants' disposition for both participant study status and the participant analysis populations.

Screened participants are defined as any participants who signed the informed consent form.

Randomized participants consist of all participants with a signed informed consent form who have had a treatment kit number allocated and recorded in the IRT database, regardless of whether the treatment kit was used.

The total number of participants in each of the following categories will be presented in the clinical study report using a flowchart diagram or summary table:

- Screened participants
- Nonrandomized but treated participants
- Randomized participants
- Randomized but not treated participants
- Randomized and treated participants
- Participants who have completed the 30-week core treatment period as per protocol
- Participants who did not complete the 30-week core treatment period, and main reasons for permanently treatment discontinuation.
- Participants who have completed the whole study treatment period including the 26-week extension period as per protocol
- Participants who did not complete the whole study treatment period, and main reason for permanent treatment discontinuation
- Participants who completed the study as per protocol
- Participants who discontinued the study by main reason for permanent study discontinuation
- Status at last study contact

For all categories of participants (except for the screened, and nonrandomized but treated categories) percentages will be calculated using the number of randomized participants as the denominator. Reasons for treatment and study discontinuation will be supplied in tables giving numbers and percentages by treatment group.

Summary of participants who discontinued treatment and/or study will be provided with reasons for discontinuation, including reasons related to COVID-19.

2.2.1 Protocol Deviations

All significant deviations, potentially impacting efficacy analyses, randomization, and drug dispensing irregularities, and other selected significant deviations will be recorded.

2.3 ANALYSIS POPULATIONS

Participants treated without being randomized will not be considered randomized and will not be included in any efficacy population.

The randomized population includes any participant who has been allocated to a randomized treatment regardless of whether the treatment kit was used.

For any participant randomized more than once, only the data associated with the first randomization will be used in any analysis population. The safety experience associated with any later randomization will be assessed separately.

The safety experience of participants treated and not randomized will be reported separately, and these participants will not be in the safety population.

2.3.1 Efficacy populations

The efficacy analysis population will be the ITT population.

2.3.1.1 Intent-to-treat population

The intent-to-treat (ITT) population is defined as all randomized participants, irrespective of compliance with the study protocol and procedures analyzed, according to the treatment group allocated by randomization.

2.3.2 Safety population

The safety population is defined as:

- Randomized population who actually received at least 1 dose or part of a dose of the IMP, analyzed according to the treatment actually received

In addition:

- Nonrandomized but treated participants will not be part of the safety population; however, their safety data will be presented separately.
- Randomized participants for whom it is unclear whether they took the IMP will be included in the safety population as randomized according to their planned treatment.

- For participants receiving 1 or more injections of efpeglenatide during the trial, regardless of being assigned to the efpeglenatide groups or not, the treatment group allocation for as-treated analysis will be included in the efpeglenatide dose group that they are exposed for longer duration. In case of a tie, the highest dose group will be used. Participants, who premature discontinued study treatment during the titration phase, will be summarized in their planned treatment group for as-treated analysis too.
- Randomized participants will be excluded from the safety population only if there is documented evidence (ie, all study dates recorded as no medication taken) that participants have not taken the study treatment. If a participants is dispensed double-blind IMP and is lost to follow-up without any documented evidence, the participants will be considered exposed.

2.4 STATISTICAL METHODS

In general, descriptive statistics of quantitative efficacy and safety endpoints (result and change from baseline) by scheduled visit will be provided on observed cases (OC), ie, only including participants having a non-missing assessment at a specific visit.

Due to study early termination, the analyses specified in this document focus on demographics, disease characteristics at baseline, exposure, participants disposition, and safety. Primary and secondary efficacy data will be descriptively summarized.

2.4.1 Demographics and baseline characteristics

Parameters described in [Section 2.1.1](#) will be summarized on the ITT population by randomized treatment group and overall using descriptive statistics.

Continuous data will be summarized using the number of available data, mean, standard deviation (SD), median, minimum, and maximum for each treatment group. Categorical and ordinal data will be summarized using the number and percentage of participants in each treatment group. Missing data will not be categorized in the summaries.

Technical formulas are described in [Section 2.5](#).

P-values on demographic and baseline characteristic data will not be calculated.

2.4.2 Extent of investigational medicinal product exposure

The extent of IMP exposure will be assessed and summarized by actual treatment within the safety population ([Section 2.3.2](#)).

2.4.2.1 Extent of investigational medicinal product exposure

The extent of IMP exposure will be assessed by cumulative exposure (participants years), duration (days), and category (weeks).

Duration of IMP exposure is defined as last dose date - first dose date + 7, regardless of unplanned intermittent discontinuations (see [Section 2.5.3](#) for calculation in case of missing or incomplete data).

Duration of IMP exposure will be summarized descriptively as a quantitative variable (number, mean, SD, median, minimum, and maximum). In addition, duration of treatment exposure will also be summarized categorically by numbers and percentages for each of the following categories and cumulatively according to these categories: 1 to 2 weeks, 3 to 4 weeks, 5 to 8 weeks, 9 to 12 weeks, 13 to 18 weeks, 19 to 24 weeks, 25 to 30 weeks, 31 to 43 weeks, 44 to 56 weeks, and >56 weeks; cumulative duration of treatment by category (weeks) will also be summarized. The duration of treatment exposure in weeks will be the duration (in days)/7 rounded to the nearest integer.

2.4.3 Analyses of efficacy endpoints

Efficacy analyses will be performed on the ITT population using efficacy assessment collected during the study, including those obtained after IMP discontinuation or introduction of rescue therapy, unless otherwise specified (see [Section 2.5.4](#)).

Descriptive summary will be provided at screening, baseline, Week 30 and Week 56 displaying observed value and change from baseline for efficacy endpoints (HbA1c, FPG, body weight and % participants achieving 7%).

In summary by visits, Week 56 data will be presented respectively:

1. Including all Week 56 visits performed per protocol as well as premature end of treatment/study visit recorded as Week 56 due to early termination.
2. Including Week 56 visits for participants who completed treatment and/or study.

2.4.4 Analyses of safety data

The summary of safety results will be presented by treatment group on the “whole on-treatment period” as defined in [Section 2.1.4](#).

General common rules

All safety analyses will be performed on the safety population as defined in [Section 2.3.2](#), unless otherwise specified, using the following common rules:

- Safety data in participants who do not belong to the safety population (eg, treated but not randomized) will be listed separately

- The potentially clinically significant abnormality (PCSA) values are defined as abnormal values considered medically important by the Sponsor according to predefined criteria/thresholds based on literature review and defined by the Sponsor for clinical laboratory tests, vital signs, and ECG (PCSA version 3 date dated 21 May 2014 effective date 24 May 2014 [[Appendix A](#)])
 - PCSA criteria will determine which participants had at least 1 PCSA during the whole on-treatment period, taking into account all evaluations performed during the whole on-treatment period, including nonscheduled or repeated evaluations. The number of all such participants will be the numerator for the whole on-treatment period PCSA percentage.
 - The treatment-emergent PCSA denominator by group for a given parameter will be based on the number of participants assessed for that given parameter in the whole on-treatment period by treatment group on the safety population.
- The analysis of the safety variables will be descriptive, and no systematic testing is planned.

2.4.4.1 Analyses of adverse events

Generalities

The primary focus of AE reporting will be on TEAEs.

If an AE date/time of onset (occurrence, worsening, or becoming serious) is incomplete, an imputation algorithm will be used to classify the AE as pretreatment, treatment-emergent, or posttreatment. The algorithm for imputing date/time of onset will be conservative and will classify an AE as treatment emergent unless there is definitive information to determine it is pretreatment or posttreatment. Details on classification of AEs with missing or partial onset dates are provided in [Section 2.5.3](#).

Incidence tables will present AEs by SOC, HLT, and PT, sorted in SOC internationally agreed order and HLT and PT sorted alphabetically for each treatment group, and the number (n) and percentage (%) of participants experiencing an AE. Multiple occurrences of the same event in the same participant will be counted only once in the tables within a treatment phase. The denominator for computation of percentages is the safety population within each treatment group.

Sorting within tables ensures the same presentation for the set of all AEs within the observation period. For that purpose, the table of all TEAEs presented by primary SOC and PT sorted by the internationally agreed SOC order and decreasing frequency of PTs within SOCs will define the presentation order for all other tables unless otherwise specified. In case of equal frequencies of PTs within a SOC, the alphabetic order will be applied. Sorting will be based on the incidence in the efpeglenatide 6 mg group.

The internationally agreed order of SOCs shown below was described in the Introductory Guide MedDRA Version 19.1, September 2016 International Conference on Harmonisation for SOC:

1. Infections and infestations
2. Neoplasms benign and malignant (including cysts and polyps)
3. Blood and lymphatic system disorders
4. Immune system disorders
5. Endocrine disorders
6. Metabolism and nutrition disorders
7. Psychiatric disorders
8. Nervous system disorders
9. Eye disorders
10. Ear and labyrinth disorders
11. Cardiac disorders
12. Vascular disorders
13. Respiratory, thoracic, and mediastinal disorders
14. Gastrointestinal disorders
15. Hepato-biliary disorders
16. Skin and subcutaneous tissue disorders
17. Musculoskeletal, connective tissue, and bone disorders
18. Renal and urinary disorders
19. Pregnancy, puerperium, and perinatal conditions
20. Reproductive system and breast disorders
21. Congenital and familial/genetic disorders
22. General disorders and administration site conditions
23. Investigations
24. Injury, poisoning, and procedural complications
25. Surgical and medical procedures
26. Social circumstances
27. Product issues

Analysis of all treatment-emergent adverse events

The following TEAE summaries will be generated for the safety population.

- Overview of TEAEs, summarizing number (%) of participants with any
 - TEAE
 - Serious TEAE
 - TEAE leading to death
 - TEAE leading to permanent treatment discontinuation
 - Discontinued per investigator decision
 - Discontinued per participant decision
 - Treatment-related TEAE
 - TEAEs of special interest (AESI)
 - TEAEs requiring specific monitoring (AERSM)
- All TEAEs by primary SOC, HLT, HLT, and PT, showing number (%) of participants with at least 1 TEAE sorted by the SOC internationally agreed order. The other levels (HLT, HLT, PT) will be presented in alphabetical order. This sorting order will be applied to all other tables by SOC, HLT, HLT, and PT, unless otherwise specified.
- Summary of common TEAEs (eg, PTs with incidence $\geq 2\%$ in any treatment group) will be presented by primary SOC and PT

Analysis of all treatment emergent serious adverse event(s)

- All serious TEAEs by primary SOC, HLT, HLT, and PT, showing the number (%) of participants with at least 1 serious TEAE.

Analysis of all treatment-emergent adverse event(s) leading to treatment discontinuation

- All TEAEs leading to treatment discontinuation per investigator decision, by primary SOC, HLT, HLT, and PT, showing the number (%) of participants
- All TEAEs leading to treatment discontinuation per investigator and/or participant decision, by primary SOC, HLT, HLT, and PT, showing the number (%) of participants

Analysis of adverse events of special interest and requiring specific monitoring

Adverse events of special interest (AESI) and adverse events requiring specific monitoring (AERSM) include AE defined in [Section 2.1.4](#) and the criteria of AESI and AERSM are in [Table 1](#).

Table 1 - Criteria for AESI and AERSM

AE Grouping	Criteria
AESI	
Pregnancy	“Pregnancy” or “Partner pregnancy” checked
Symptomatic Overdose	“Overdose” checked and symptomatic (AEOVSYMP) = “Yes”
Increase in ALT >3ULN	“ALT Increase” checked and Yes to the question “Is the event an AESI?” in eCRF form “Adverse Events”
AERSM	
Severe GI event	AE severity = “severe” using CMQ
Severe hypoglycemia	Any hypoglycemia event which required assistance (from hypoglycemia page)
Pancreatic event	Cases reported in pancreatic specific eCRF page or AE Category = “Pancreatic Neoplasm”
Selected cardiovascular event	Cases reported in the following specific eCRF pages: - ‘Suspected or confirmed MI/Unstable Angina’ - ‘Suspected or confirmed cerebrovascular event’, - ‘Suspected or confirmed heart failure’ led to unplanned hospitalization, led to urgent/unscheduled visit to emergency room or an urgent/unscheduled outpatient heart failure treatment unit, or infusion center, or office/practice visit, not followed by hospitalization, or occurred while patient was hospitalized for another reason - Primary cause of death in eCRF “Death (CV)” as Acute MI, Sudden cardiac death, Heart failure or cardiogenic shock, Stroke, Complication of cardiovascular procedure, Other cardiovascular cause, or Undetermined cause of death
Calcitonin and thyroid C-cell neoplasm	Using Calcitonin increase CMQ Using Medullary thyroid cancer CMQ
Acute renal failure	Using Acute renal failure CMQ
Severe injection site reaction	Intensity = “Severe” + Using Injection site reaction_ CMQ.
Severe allergic reaction	Intensity = “Severe” + CMQs for anaphylactic reaction, angioedema, severe cutaneous adverse reaction, anaphylactic/anaphylactoid shock conditions (under SMQ “Shock”), and hypersensitivity
Severe immune complex disease	Intensity = “Severe” using Immune complex disease CMQ
Diabetic retinopathy complications	Cases reported in eCRF “Diabetic Retinopathy Complementary Form”

The following TEAE summaries will be generated for the safety population:

- All AESI by prespecified grouping and PT, showing number (%) of participants with at least 1 AESI, with PTs sorted by decreasing order in Efpeglenatide 6 mg group.
- All AERSM by prespecified grouping and PT, showing number (%) of participants with at least 1 AERSM, with PTs sorted by decreasing order in Efpeglenatide 6 mg group.

Analysis of adjudicated events

All events of death, selected cardiovascular events (MI, stroke, unstable angina leading to hospitalization, and heart failure leading to hospitalization), any pancreas-related events, and other selected AEs (as defined in the CEC charter) will be reviewed, assessed, and adjudicated by CEC.

The events sent for adjudication, will be presented in the listings, which include at least the following information, sorted by treatment, participant identification, and onset date: treatment, participant identification, country, age, gender, race, primary SOC, PT, reported term, onset date, study day (relative day to the start date of IMP), AE duration, duration of exposure, intensity, corrective treatment, action taken with IMP, relationship to IMP/NIMP/study procedures, outcome, date of death (if any), seriousness, seriousness criteria.

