| AEs | 
All AEs will be coded to a "LLT", "PT", "HLT", and "HLGT" and associated "SOC" using the version of MedDRA currently in use by the Sponsor at the time of database lock.
 
Adverse event incidence tables will be presented by primary SOC (sorted by internationally agreed order), HLGT, HLT and PT (sorted in alphabetical order) for each treatment group, showing the number (n) and percentage (%) of participants who experienced an AE.
 
The primary focus of AE reporting will be on TEAEs. Pretreatment and posttreatment AEs will be described separately.
 
Adverse event incidence tables will be provided by treatment group for all types of TEAEs: all TEAEs, all treatment-emergent SAEs, all TEAEs leading to permanent treatment discontinuation, and all TEAEs leading to death.
 
Tables will be presented for the "30-week core on-treatment period" and for the "whole on-treatment period including the 26-week controlled Treatment Extension Period".
 
AE, SAE, and AEs leading to death tables will be presented for the 30-week on-study period too.
 |
| Hypoglycemia | 
The number (%) of participants with at least 1 hypoglycemic event during the on-treatment period will be assessed per type of hypoglycemic event (see Section 8.2.5) and according to time of occurrence (nocturnal [ie, 00:00 to 05:59 am], daytime [06:00 to 23:59]). Documented hypoglycemia (symptomatic or asymptomatic) will be also evaluated for the more stringent SMPG threshold of <3.0 mmol/L (<54 mg/dL).
 
Summaries will be presented overall and by type of event for each treatment group.
 
The total number of events (per participant-years) will be computed and summarized overall and by type of event for each treatment group.
 
Similar summaries will be also provided for the 30-week core on-treatment period.
 |

| Endpoint | Statistical Analysis Methods |
|---------------------------------|--|
| Vital signs and laboratory data | For quantitative safety parameters based on central laboratory/reading measurements, descriptive statistics will be used to summarize results and changes from baseline values by visit and treatment group. |

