1.4 STUDY PLAN

[figure not shown]
This is a multicenter, 56-week, randomized, double-blind, placebo-controlled Phase 3 study consisting of 4 study periods:

- A 2-week Screening Period (11 to 14 days)

- A 30-week double-blind, placebo-controlled Core Treatment Period, for efficacy and safety assessment
- A 26-week double-blind, placebo-controlled Treatment Extension Period; participants will remain on the randomized investigational medicinal product (IMP) regimen
- A 6-week Follow-up Period to collect posttreatment safety information for all participants after last dose of IMP

The maximum study duration per participant will be 64 weeks with treatment lasting for 56 weeks (a 30-week core treatment period and a 26-week extension period). The graphical study design is shown in [Figure 1](#).

Figure 1 - Study Design Overview

The end of the study is defined as the date of the last visit of the last participant in the study.

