2.1.4 Safety endpoints

The safety analysis will be based on the reported adverse events (AE), hypoglycemia and other safety information, such as clinical laboratory data, vital signs, and ECG.

Observation period

The observation period related to treatment will be divided into 3 main segments:

- The **pre-treatment** period is defined as the time from informed consent up to the time of first injection of IMP
- The whole **on-treatment** period is defined as the time from the first injection of the IMP up to 30 days (7 days for hypoglycemia) after the last injection of the IMP
 - The 30-week core on-treatment period is defined as the time from the first injection of IMP up to Visit 9 (Week 30) (or Day 210 if Visit 9 [Week 30] visit is missing) or up to 30 days (7 days for hypoglycemia) after the last injection of IMP, whichever comes earlier
- The **post-treatment** period is defined as the period from the end of the whole on-treatment period.

The **on-study observation period** is defined as the time from first injection of IMP up to either the last protocol-planned visit or the date of last available information if participants discontinue the study prematurely (ie, the date collected on e-CRF page “Completion of End of Study/Follow-up”), whichever is later.

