2.1.4.1 Adverse event observation period

- **Pretreatment AEs** are AEs that developed or worsened or became serious during the pre-treatment period
- **Treatment-emergent AEs (TEAEs)** are AEs that developed or worsened or became serious during the on-treatment period
- **Posttreatment AEs** are AEs that developed or worsened or became serious during the post-treatment period

All AEs (including SAEs, AEs of special interest, and AEs requiring specific monitoring) will be coded to a lower-level term (LLT), preferred term (PT), high-level term (HLT), high-level group term (HLGT), and associated primary system organ class (SOC) using the version of MedDRA currently in effect at the time of database lock.

Adverse events of special interest (AESIs) include the following:

- Pregnancy of a female participant entered in a study as well as pregnancy occurring in a female partner of a male participant entered in a study with IMP/NIMP.
- Symptomatic overdose (serious or nonserious) with IMP/NIMP
- Increase in alanine aminotransferase (ALT) $>3 \times$ upper limit normal (ULN)

Adverse events requiring specific monitoring include the following terms:

- Severe gastrointestinal (GI) events

- Severe hypoglycemia
- Pancreatic events (including abnormal values of pancreatic enzymes, pancreatitis and pancreatic neoplasm)
- Selected cardiovascular events (CV death, MI, stroke, heart failure leading to hospitalization, unstable angina, and transient ischemic attack (TIA))
- Calcitonin increase (≥ 5.9 pmol/L (20 pg/mL)) and thyroid C-cell neoplasm
- Acute renal failure
- Diabetic retinopathy complications
- Severe injection site reaction
- Severe allergic reactions
- Severe immune complex disease

Independent Clinical Endpoint Committee(s) [CEC(s)] will review, assess, and/or adjudicate all events of death, selected CV events, and pancreatic events.

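### Every adverse-event table in the SAP stops 30 days after the last injection, so events starting later appear in no table, and the loss of two protocol-planned safety outputs is not declared

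*SAP*

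**What the plan says.** SAP 1.4 gives the follow-up its purpose: "A 6-week Follow-up Period to collect posttreatment safety information for all participants after last dose of IMP". Protocol 8.3.1 collects AEs from consent to the participant's end of study.

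SAP 2.1.4 runs the whole on-treatment period "up to 30 days (7 days for hypoglycemia) after the last injection of the IMP". SAP 2.4.4 presents safety results on that period. SAP 2.1.4.1 says that treatment-emergent AEs "are AEs that developed or worsened or became serious during the on-treatment period", and that posttreatment AEs "are AEs that developed or worsened or became serious during the post-treatment period". SAP 2.1.4 also defines an on-study observation period, which SAP 2.1.4.2 uses to classify deaths.

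SAP 2.4.4.1 states that "The primary focus of AE reporting will be on TEAEs" and introduces its tables with "The following TEAE summaries will be generated for the safety population".

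Protocol 9.4.2, Table 7, has the same focus on TEAEs but adds two outputs: "Pretreatment and posttreatment AEs will be described separately" and "AE, SAE, and AEs leading to death tables will be presented for the 30-week on-study period too". Protocol 9.4.2 defines that on-study period as running to Week 30 whether or not IMP is still being taken.

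SAP 1.5, on modifications to the protocol's statistical section, reads as not applicable. SAP 1.6 says that, because of early termination, the planned efficacy evaluations were not performed and PK and ADA samples were not analyzed. It calls the document a simplified SAP for a synopsized report.

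**The concern.** The SAP defines a posttreatment AE category, and the study has a follow-up period meant to fill it, but no table or listing uses the category. A non-fatal SAE that is not sent for adjudication and starts on Day 31 or later after the last dose reaches no specified output. The same holds for a non-adjudicated AESI or AERSM. Pregnancy is one example: it is an AESI, its details are collected to Visit 14 (Protocol 8.3.5), and one arising after Day 30 would be in no AESI table.

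Safety is a stated secondary objective (SAP 1.2.2) and one of the areas the shortened SAP says it concentrates on (SAP 2.4). The data are already collected. A reader of the report could take the serious-event table as complete, since nothing in SAP 1.5 or 1.6 says that the posttreatment and on-study outputs were removed.

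**Working it through.** **1. Which outputs cover which period**

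| Output | Protocol 9.4.2, Table 7 | SAP 2.4.4 to 2.4.4.3 |
|---|---|---|
| AE, SAE and discontinuation tables, on treatment | Yes | Yes |
| AESI and AERSM tables | Not specified in Table 7 | Yes, under the TEAE summaries |
| Posttreatment AEs | Described separately | None specified |
| AE, SAE and fatal-AE tables, 30-week on-study period | Yes | None specified |
| Deaths | In the fatal-AE tables | Listing, all screened participants |
| Events sent for adjudication | Not specified in Table 7 | Listing, no time limit stated |

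The AESI and AERSM bullets begin with the word All, but they stand under the TEAE introduction and under the period rule in SAP 2.4.4. They are therefore treatment-emergent tables too.

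**2. Timing of the end-of-study visit**

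Inputs: end of treatment on Day 392 and end of study on Day 434 ± 7 (Schedule of Activities, in both documents).

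- Nominal follow-up: 434 − 392 = 42 days. This reproduces the stated 6 weeks.
- Visit range: 42 − 7 = 35 to 42 + 7 = 49 days after the last dose, always beyond 30.

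**3. Uncovered time for a completer**

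Formula: (visit day − 30) / visit day.

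- Earliest: (35 − 30)/35 = 5/35 = 14%
- Nominal: (42 − 30)/42 = 12/42 = 29%
- Latest: (49 − 30)/49 = 19/49 = 39%

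**4. Uncovered time for an early stopper (illustration)**

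Protocol 7.1.1 asks participants who stop IMP to continue visits to Week 56. Suppose the last dose is on Day 29 and follow-up reaches Day 392.

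- The window closes on Day 29 + 30 = 59.
- Untabulated days: 392 − 59 = 333, and 333/392 = 85% of the scheduled days.
- The protocol's 30-week on-study tables would have recovered 210 − 59 = 151 of these days. The protocol left the rest to the separate description of posttreatment AEs.

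For other assumed last-dose days, uncovered off-drug time is (392 − d − 30)/(392 − d):

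| Last dose, day d | Uncovered / off-drug days | Share |
|---|---|---|
| 84 | 278 / 308 | 90% |
| 168 | 194 / 224 | 87% |
| 210 | 152 / 182 | 84% |
| 301 | 61 / 91 | 67% |

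The documents give neither the number of early stoppers nor their actual follow-up. These rows show how the rule behaves; they do not estimate what was lost.

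**The case against.** The strongest reply is that this is a simplified, descriptive SAP for a terminated study. SAP 1.6 says it is simplified, and SAP 2.4.4 states openly that safety is summarized on the whole on-treatment period, so nothing is concealed. Deaths are listed without a 30-day limit. Events sent for adjudication (selected cardiovascular, pancreatic and other charter-defined events) are listed by treatment with onset date and seriousness. The protocol promised only that posttreatment AEs be described, which a listing would satisfy. Much of this stands, and it limits the size of the problem. It does not supply an output for non-fatal, non-adjudicated events after Day 30, and simplification in general is not a statement that these particular outputs were dropped.

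Three stronger readings are tempting, and the documents do not support them:

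- A reader might infer that anything found at the end-of-study visit, including its laboratory tests, can never be tabulated. AEs are classified by when they developed, worsened or became serious, not by when they were found. An event reported at that visit with onset by Day 30 is still a TEAE, and incomplete onset dates default to treatment-emergent unless they show otherwise (SAP 2.4.4.1 and 2.5.3).
- A reader might infer that the omission favors the higher doses, because Protocol 4.3 calls nausea and vomiting dose related. No discontinuation rates by arm are given, and the same section says that these events generally decreased after the first injection. An imbalance between arms is conjecture.
- A reader might infer from the contraceptive and pregnancy-testing precautions of at least 5 weeks that the 30-day window is itself wrong. Those precautions do not establish how long an AE window should be.

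**Conclusion.** The point holds for events that start, worsen or become serious on Day 31 or later after the last injection. Two safety outputs planned in Protocol Table 7 are missing from the SAP, and SAP 1.5 and 1.6 do not name them as dropped. For a completer the uncovered time is nominally 12 of 42 days (range 5 of 35 to 19 of 49). For an early stopper it can be most of the remaining follow-up; the 333 of 392 days above assumes a last dose on Day 29 and follow-up to Day 392. Actual follow-up may be shorter, because the sponsor terminated the study on 09 September 2020 (SAP 1.1).

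The 30-day definition of treatment emergence is not in dispute, and the on-treatment tables are unaffected. This is a gap in reporting data already collected. The sponsor should close it, since safety is a stated objective and the remedy is cheap.

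**What to change.** In SAP 2.4.4.1, do one of the following:

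- add by-arm summaries of posttreatment AEs and posttreatment SAEs, with onset (or worsening, or becoming serious) from Day 31 after the last injection to the end of the on-study period, including posttreatment AESI and AERSM counts; or
- add one by-arm table of all SAEs over the on-study observation period already defined in SAP 2.1.4.

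In either case, state in SAP 1.6 any protocol safety output that is still dropped, with the reason. The second option alone leaves non-serious posttreatment AEs undescribed, so it would need that statement.

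Cost: SAP wording and one to three standard tables, using existing data and definitions. The downside is slightly more output, including some events unlikely to be drug related.
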